# A Randomized Trial of Preoperative Prophylactic Antibiotics Prior to Kidney Stone Surgery (Percutaneous Nephrolithotomy [PCNL])

NCT #02384200

Document Date - July 3, 2016

This study will be a multi-institutional randomized, controlled clinical trial of a course of a 1 week course of preoperative nitrofurantoin monohydrate/macrocrystalline capsules (trade name Macrobid) 100 milligrams twice daily leading up to PCNL. The control group will be no preoperative oral antibiotics. The participating institutions are academic medical centers in the United States and Canada that are part of the EDGE (Endourologic Disease Group of Excellence) research consortium, a research collaborative that has the goal of producing high quality, multi-institutional studies of nephrolithiasis. Separate IRB approvals will be obtained at each institution. UCSD will be the coordinating institution. Member institutions of EDGE maintain frequent email contact with one another and hold a monthly teleconference to discuss safety updates, interim results, issues with accrual, and modifications to research protocols and consents (if necessary).

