### Treatment Assignment:

Patients will be assigned to control or intervention arm based on a predetermined allocation sequence that will be generated by a computerized random number generator. Patients will be stratified by institution in permuted blocks of varying size. Only study staff at the coordinating institution (UCSD) will have access to the full allocation sequence. i.e. no clinical staff involved in recruiting and consenting patients for the study at UCSD or other participating institutions will have knowledge of the allocation sequence at their institution prior to enrollment of each patient. To further aid allocation concealment, the block size will be varied.

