### b. Data Collection

Data will be collected by each participating site and entered into a designated and shared REDCap (Research Electronic Data Capture) database. All patient specific information will be de-identified and the database will be password protected with access rights restricted to the lead investigator or their team at each site. Data collectors will be blinded from treatment allocation.

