### c. Data Handling

The electronic data will be stored in the external REDCap database. This database will be saved at a separate server that allows the study staff from non-UCSD sites to contribute their database. Study staff will create the database and is responsible for analyzing the study data. The coordinator at each site will perform data entry.

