#### d. Data Analysis

The summary statistics will be used to describe the data. Mean/95% confidence intervals will be reported for continuous variables, and frequency/percentage will be reported for nominal variables. The primary outcome, rate of postoperative sepsis, and the corresponding 95% confidence interval (CI) will be reported, and compared between the intervention and control groups at the for the postoperative period using a Chi-squared test. Secondary outcomes will include rate of nonseptic bacteruria, stone-free rate, and LOS and will be compared with using Chi-squared tests or t-test as indicated. The patient characteristics and outcomes between those who have one-year follow up records and those who do not will also be investigated. Using 2-sided P values, statistical significance will be set at  $p \le 0.05$ .

Sepsis will be defined by the 2012 International Guidelines for Management of Severe Sepsis and Septic Shock where 2 or more of the following variables are present and temporally associated

- Temp > 38.3 C or <36 C
- Heart Rate > 90/min (at least 12 hrs after surgery)
- Respiratory Rate > 20/min (at least 12 hrs after surgery)
- Altered mental status: defined as lack of orientation to either name, place, or time/date.
- Systolic Blood Presure (SBP) < 90 mmHg, Mean Arterial Pressure < 70 mmHg, or SBP decrease >40 mmHg in adults
- WBC >12000 or < 4000

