# e. Feasibility and Time Frame

This study enrollment period will be 2 years, with presumed enrollment expected to be completed prior to that date. Each site is a high-volume stone center that performs more than 30 PCNLs per year.

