### g. Limitations

The inclusion of a placebo pill would strengthen the study but was not able to be included due to logistical difficulties with obtaining a placebo of identical appearance that would have been adequate for blinding. Furthermore, there is little benefit of a "placebo effect" for the objective outcomes that we seek to study which are signs and symptoms of sepsis and septic shock.

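### Interim results are an agenda item on the monthly call of the EDGE institutions, which include the recruiting sites; the plan does not limit them to pooled data and has no interim provision

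*Combined protocol and SAP*

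**What the plan says.** The opening study description names the participating institutions as part of the EDGE consortium. It says that EDGE members "hold a monthly teleconference to discuss safety updates, interim results, issues with accrual, and modifications to research protocols and consents (if necessary". Interim results are therefore an agenda item of their own, apart from safety and accrual, and protocol modifications are on the same agenda.

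Section d, Data Analysis, says that the sepsis rate will be "compared between the intervention and control groups at the for the postoperative period using a Chi-squared test". On the threshold it says "Using 2-sided P values, statistical significance will be set at" p ≤ 0.05. It gives no number or timing of looks, no stopping boundary and no division of the 0.05. It also does not say that no interim comparison will be made.

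Four other statements bear on who may see what:
- Section g, Limitations: "The inclusion of a placebo pill would strengthen the study but was not able to be included due to logistical difficulties".
- Section b, Data Collection: "Data collectors will be blinded from treatment allocation".
- Treatment Assignment: the full allocation sequence is held by study staff at the coordinating institution. It is withheld before each enrolment, so that "no clinical staff involved in recruiting and consenting patients" know it in advance.
- Section c, Data Handling: "Study staff will create the database and is responsible for analyzing the study data", with no statement of when they analyse or who receives the results.

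**The concern.** Two separate harms are possible, and both depend on by-arm results reaching the call.

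The first is operational bias. Without a placebo, the treating team can know which arm a patient is in. If the team also learns which arm is ahead, it has both pieces of information needed to act differently by arm. Concealed allocation stops staff from steering a patient to an arm, but it does not stop a change in which patients are offered the trial. Several outcomes leave room for discretion. Length of stay follows each site's usual discharge practice, stone-free status may be judged on CT, plain radiograph or ultrasound, and laboratory work beyond the routine tests depends on the patient's clinical course.

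The second is the error rate of the final test. If a by-arm comparison seen during the trial could lead to stopping or to a change in design, a final test at the full 0.05 no longer has a 5% false-positive rate.

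**Working it through.** **Step 1. Do the existing safeguards cover accumulating results?**

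| Safeguard (section) | What it protects | Does it cover by-arm outcomes on the call? |
|---|---|---|
| Restricted allocation sequence (Treatment Assignment) | The next assignment, before enrolment | No |
| Blinded data collectors (b) | Recording of individual data | No; call participants are not mentioned |
| Study staff analyse (c) | Names who analyses | No; timing and recipients are not stated |
| Same day-of-surgery IV regimen in both arms (Investigational portion of treatment) | Comparability of perioperative treatment | No; it does not govern the flow of information |
| Objective outcomes (g) | Answers a concern about placebo effect | No |

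None of these says what form of interim results may reach the call.

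**Step 2. Size of the error-rate effect, under a stated condition.** The plan has no figure to reproduce: the supplied text gives no sample size, event rate or number of looks. The only numerical input from the documents is the two-sided 0.05 in section d. Everything else here is an assumption.

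Assume one by-arm look at half of enrolment, tested at 0.05, with the trial able to stop on a positive result, and then the final test at 0.05. Under no true difference, using the normal approximation:

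- Correlation of the two test statistics = √(0.5/1) = 0.707.
- False-positive rate = 1 − P(|Z₁| ≤ 1.96 and |Z₂| ≤ 1.96).
- Numerical integration gives 0.0831. A separate simulation of 400,000 trials gives 0.0827. Its standard error is √(0.083 × 0.917 / 400,000) ≈ 0.0004, so the two agree.
- Plausibility check: the result must lie between 0.05 (perfectly correlated tests) and 1 − 0.95² = 0.0975 (independent tests). It does.
- Excess over nominal: 8.3% − 5% = 3.3 percentage points.

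**Step 3. The same scenario with the planned chi-squared test.** This used 200,000 null trials in each of nine settings, with assumed total sizes of 100, 200 and 400 and assumed sepsis rates of 10%, 15% and 25% in both arms.

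| Tests | False-positive rate across the nine settings |
|---|---|
| Final test only | 4.9% to 5.5% |
| Look at half of enrolment, then final | 8.2% to 9.2% |

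The normal approximation is therefore not an upper bound.

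**Step 4. The benign cases.** If results on the call are pooled, or if looks cannot affect the trial, the rate stays at about 5%. By-arm looks that cannot affect stopping or design still leave the operational bias.

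**The case against.** The strongest reply is that the sentence may not be about this trial. Its subject is the consortium's members, it speaks of research protocols and consents in the plural, and it follows a general description of EDGE. On that reading it describes a standing call. Section d, with one comparison and no looks, would ordinarily be read as a single final analysis. The supplied text also has lettered sections that start at b and contains no sample-size section, so monitoring text may exist in a part not supplied.

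Much of this stands. The documents do not say that results are by arm, tested, reviewed every month or used to stop, so the point can only be a request to set a limit. What does not stand is the idea that nothing needs changing. The sentence appears in this trial's own description with no exception for this trial, and interim results are listed separately from safety and accrual, so the phrase cannot simply be read as either.

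A reader might go further and infer that about 24 monthly calls over 2 years mean 24 tests at 0.05, and hence a false-positive rate near 26%. The documents do not support that. They plan no monthly test and no stopping on one, and section e, Feasibility and Time Frame, says: "This study enrollment period will be 2 years, with presumed enrollment expected to be completed prior to that date". Nor does any section mention enlarging the trial and retesting after a non-significant result, so error rates for that scenario have no basis here.

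**Conclusion.** The point holds as an unlimited statement that needs a limit. The plan lets interim results go, in unspecified form, to a group that includes the recruiting sites and can discuss protocol modifications, in a trial without placebo and with no interim provision in its analysis section.

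The operational-bias risk requires only that by-arm results reach the call; the documents give no basis for putting a number on it. The error-rate risk further requires that those results can affect stopping or design. On the assumptions above, one tested look at half of enrolment would give about 8.3%, or 8.2% to 9.2% with the chi-squared test. These figures show scale and are not this trial's error rate. It would be wrong to conclude that the trial's error rate is inflated or that by-arm data were shared. Rating: cheap improvement.

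**What to change.** In the opening study description, replace *interim results* with *data completeness and outcome data pooled across arms*, and keep safety updates and accrual on the call. Add: *No by-arm comparison of sepsis or the secondary outcomes will be shown to recruiting or treating staff before database lock. This does not restrict action on a safety concern.*

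In section d, Data Analysis, add: *There is one final efficacy analysis, at two-sided 0.05, when planned enrolment is complete.*

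The cost is a few sentences of text, with no added patients or visits. The downside is that investigators do not see by-arm results while the trial is running.

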### Treatment Assignment:

Patients will be assigned to control or intervention arm based on a predetermined allocation sequence that will be generated by a computerized random number generator. Patients will be stratified by institution in permuted blocks of varying size. Only study staff at the coordinating institution (UCSD) will have access to the full allocation sequence. i.e. no clinical staff involved in recruiting and consenting patients for the study at UCSD or other participating institutions will have knowledge of the allocation sequence at their institution prior to enrollment of each patient. To further aid allocation concealment, the block size will be varied.

# Standard of care procedures:

Patients will be identified based on clinic visits or hospital admission. All patients will be counseled on standard treatment options— extracorporeal shock wave lithotripsy (ESWL), percutaneous nephrolithotomy (PCNL) and ureteroscopy (URS). The discussion regarding treatment options and subsequent care will not deviate from routine care. Patients consenting for PCNL will be considered for enrollment into the study and will be enrolled to have data collected prospectively. Patients will be consented prior to prescription of antibiotics and to the surgery for collection of demographics, disease, perioperative, and postoperative data. Abdominal pelvic computed tomography (CT), if not already obtained, will be used to delineate pre-operative stone size and for preoperative planning. If the patient does not consent to the study the use of antibiotics will be based on the routine clinical practice of the treating urologist. Both prophylaxis with preoperative antibiotics and no prophylaxis (i.e. periprocedural only) are considered standard of care and this study will examine the difference between these two common practices.

### Investigational portion of treatment:

Patients randomized to the intervention arm will be prescribed nitrofurantoin monohydrate/macrocrystalline 100 mg twice daily for 7 days prior to PCNL with the final day of prophylactic course being 1 day prior to surgery. Nitrofurantoin monohydrate/macrocrystalline is currently indicated for the treatment of acute uncomplicated urinary tract infections. Antibiotics the day of surgery will be a dose of ampicillin IV (2 g) and gentamicin IV (5 mg/kg) within 120 minutes of surgery start time. Patients with penicillin allergy will receive vancomycin IV (1 g) instead of ampicillin and patients with gentamicin/aminoglycoside allergy will receive ceftriaxone IV (2 g) instead of gentamicin. Postoperative antibiotics in the absence of infection will be <24 hours of IV antibiotics. Control patients will receive perioperative ampicillin IV (2 g) and gentamicin IV (5 mg/kg) (or vancomycin(1 g) /ceftriaxone (2 g), if indicated) as in the intervention arm, but control patients will not be prescribed a course of preoperative oral antibiotics. Central randomization will take place with UCSD as the lead site. Randomization will occur in block randomization in block sizes of 4.

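### The protocol gives two incompatible block-size rules for randomization: varying sizes within institution in one section, blocks of 4 in another

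*Combined protocol and SAP*

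**What the plan says.** The Treatment Assignment section states the rule twice. First: "Patients will be stratified by institution in permuted blocks of varying size". Then, with its purpose: "To further aid allocation concealment, the block size will be varied". It also restricts the full sequence to study staff at the coordinating institution, so that recruiting staff do not know the next assignment before enrolling a patient.

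The section headed Investigational portion of treatment says "Central randomization will take place with UCSD as the lead site" and then "Randomization will occur in block randomization in block sizes of 4". It gives one size and does not mention variation.

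Three other points bear on this:

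- **Ratio.** There are two arms ("Patients will be assigned to control or intervention arm based on a predetermined allocation sequence"), but no allocation ratio is stated.
- **Visibility of past assignments.** In the intervention section, "control patients will not be prescribed a course of preoperative oral antibiotics". Under g. Limitations, "The inclusion of a placebo pill would strengthen the study but was not able to be included". The oral course is therefore open-label to those who prescribe it.
- **Patients per site.** Section e (Feasibility and Time Frame) gives surgical volume per site and a two-year enrolment period, but neither enrolment per site nor the number of sites.

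**The concern.** A list built only from blocks of 4 does not have varying block sizes. Someone building or auditing the lists could not tell from this document which rule applies, and a results paper that took its methods from the wrong section would misreport the randomization.

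The disagreement touches a safeguard that the plan chose for itself. Restricting access to the list stops staff from reading it. It does not stop them from deducing an assignment from earlier ones, if the block size is known and the earlier arms can be seen. Here the arms are visible to prescribers, and the number 4 is printed in the protocol. The protocol treats both antibiotic practices as standard of care, so a urologist with a preference could let a foreseen assignment influence when, or whether, a patient is enrolled. Blinding the data collectors acts after enrolment and does not address this.

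**Working it through.** The plan states no predictability figure, so there is none to reproduce.

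**Inputs.** Block size 4 comes from the intervention section; blocks within institution come from Treatment Assignment. Assumptions: 1:1 allocation, sites of various sizes n, and an observer who knows the block size and every earlier assignment at the site.

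**One fixed block of 4 at 1:1.** There are 6 equally likely sequences. An assignment is certain once one arm has received its 2 patients.

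- In 4 of the 6 sequences only the 4th assignment is forced. In the other 2 (AABB, BBAA) the 3rd and 4th are.
- Expected certain per block = (4 × 1 + 2 × 2)/6 = 4/3. As a share, (4/3)/4 = 33.3%.
- The best guess is correct with probability 1/2, 2/3, 2/3 and 1 at positions 1 to 4. The sum is 17/6, and (17/6)/4 = 70.8%.

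**A site of n patients.** Write n = 4q + r.

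- Certain share = (q × 4/3 + d)/n, with d = 0, 0, 0, 1/3 for r = 0, 1, 2, 3.
- Best-guess accuracy = (q × 17/6 + g)/n, with g = 0, 1/2, 7/6, 11/6.

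| n | Expected number certain | Certain share |
|---|---|---|
| 3 | 1/3 | 11.1% |
| 6 | 4/3 | 22.2% |
| 7 | 5/3 | 23.8% |
| 8 | 8/3 | 33.3% |
| 9 | 8/3 | 29.6% |
| 10 | 8/3 | 26.7% |
| 11 | 3 | 27.3% |
| 30 | 28/3 | 31.1% |
| 40 | 40/3 | 33.3% |

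From n = 8 upward the share stays between 26.7% (the minimum, at n = 10) and 33.3%. Below 8 it depends on the last block: 4 patients give 33.3% and 5 give 26.7%, but 1 or 2 give 0%. Best-guess accuracy is (17/3 + 7/6)/10 = 68.3% at n = 10 and (7 × 17/6 + 7/6)/30 = 70.0% at n = 30.

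**Varied sizes, n = 10.** The plan lists no sizes, so 4/6 and 4/6/8 are illustrations, with each size equally likely. The observer knows the possible sizes but not their order. Exact recursion over all histories gives:

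| Sizes | Certain share | Best guess correct |
|---|---|---|
| 4 only | 26.7% | 68.3% |
| 4 or 6 | 6.0% | 67.9% |
| 4, 6 or 8 | 2.4% | 65.9% |

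A partial hand check for 4/6: early certainty arises only when a third patient in one arm rules out size 4.

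- A first block of 6 (probability 1/2, 20 sequences) opens with three alike in 2/20, so probability 0.05. Positions 4, 5 and 6 are then certain, contributing 0.15.
- It splits 3:1 over its first four places, without opening with three alike, in 6/20, so probability 0.15. Positions 5 and 6 are then certain, contributing 0.30.
- Positions 7 to 10 add 0.15 by the recursion. The total is 0.60 of 10, or 6.0%.

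**What the comparison shows.** Varying the size removes most certain knowledge. It removes little of the advantage of an informed guess.

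**The case against.** The strongest reply is that the percentages describe a scheme that neither section sets out in full. Stratification by institution comes from one section and the fixed size from the other, the ratio is assumed, and no passage says that any one recruiter sees every assignment at a site. That stands, and it is why the figures are only a conditional note. It does not remove the contradiction on block size.

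A second reply is that the certainty figure flatters the varied-size rule, since best-guess accuracy at 10 patients falls only from 68.3% to 67.9% or 65.9%. This also stands. Varying the size is worthwhile against certain knowledge, but is not a full defence against guessing.

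Three stronger readings are tempting, and the documents support none of them:

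- **That about 30% of assignments were in fact foreseeable, or that the comparison is biased.** Nothing shows that fixed blocks were used or that anyone exploited them.
- **That the two sections also disagree on stratification.** The intervention section is only silent on institution. Central randomization says who runs the process, and fits site-stratified lists held centrally.
- **That restricted list access or objective outcomes settle the matter.** The first does not prevent deduction from visible assignments. The second is offered in the Limitations section as an answer to the placebo effect, not to selection at enrolment.

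**Conclusion.** The contradiction is certain, is in current text, and has to be reconciled whichever rule was used. If Treatment Assignment was followed, the harm is limited to a false statement in the intervention section. If fixed blocks of 4 ran within site, a safeguard that the plan expressly adopts was weakened.

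In that second case the certain share is 33.3% for complete blocks and 26.7% to 33.3% at sites with 8 or more patients. This rests on 1:1 allocation, a known block size, full knowledge of the site's earlier assignments, and a site size that the documents do not give. It measures what could be predicted. It does not estimate bias.

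**What to change.** 1. The coordinating centre confirms from its records how the lists were generated (fixed or varied size, within site, and in what ratio) and makes the two sections agree.
2. If sizes were varied within site, delete the block size of 4 from the intervention section.
3. If fixed blocks of 4 were used, do not simply delete the phrase. Record the fixed-block period and report it with the results, whether or not enrolment is still open. If enrolment is open, also generate the remaining site lists with varied sizes. If an open block is allowed to finish, the rest of that block stays predictable.
4. In every case, state the allocation ratio and keep the sizes in use out of text that sites can see. The choice of sizes is left to the coordinating centre.

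**Cost.** One check of the lists and a protocol amendment, which may need handling at every site because "Separate IRB approvals will be obtained at each institution". New lists are needed only if fixed blocks were used and enrolment continues. Larger blocks slightly raise the greatest possible imbalance within a site, which at 1:1 is half the largest block: 2 patients with blocks of 4, 3 with blocks up to 6, and 4 with blocks up to 8.
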